2.3 Evaluation of The Accuracy and Reliability of Automated Cephalometry Analysis Software

A study by Anuwangnukroh et al. (2018) evaluated the reliability of the cephalometric analysis using the dental imaging software (Carestream Dental). They found that the automated cephalometric analysis software has significant difference of more than 2 degrees when compared to the manual hand-based analysis. They also found that the differences come mainly from the angular parameters.

On the other hand, another study by Katyal et al., (2022) investigated the automated tracing software using the WebCeph software. They found there is no significant difference in the skeletal, dental and the soft-tissue parameters between the two methods. However, it takes shorter time for the automated tracing to analyse the data when compared to the manual tracing where the time taken is 30.2 ± 6.4 s and 472 ± 40.4 s respectively (Katyal et al., 2022). Another study by Tsolakis (2022) compared the digital automatic method and digital manual method of cephalometric analysis and found small difference between the two methods but it was not clinically significant.

3.0 Materials and Methods

3.1 Study Population

This prospective study includes 40 cephalometric radiographs of orthodontic patients seen in Orthodontic Specialist Clinic of Kulliyyah of Dentistry, IIUM Kuantan.

The sample size calculation was done with a significance level of 0.05 and a power value of 95%. A sample of a minimum of 37 radiographs was needed.

3.2 Inclusion criteria:

- Pretreatment OR post-treatment lateral cephalometric radiographs
- Orthodontic patients treated at the Orthodontic Specialist Clinic, IIUM
- Radiographs obtained between January 2023 and June 2023
- High-quality cephalograms without flaws affecting anatomical landmark positions

3.3 Exclusion criteria:

- Patients with surgical rigid fixations visible on radiographs
- Presence of orthodontic appliances on radiographs
- Presence of dental prostheses on radiographs
- Patients with syndromes and craniofacial deformities.

3.4 Methodology

Ethical approval will be obtained before the commencement of the study. Forty cephalometric radiographs will be selected. Calibration will be done prior to landmark identification to ensure agreement between the examiners.

For manual tracing, 18cm x 24cm of radiographic film images of lateral cephalograms will be obtained and traced manually on a view box using transilluminated light under dark room. Each cephalograms will be secured over the view box first, and then a sheet of matte acetate tracing paper sized 22cm x 28cm are taped over the radiographic film. Three orientation marks will be placed as a reference point over the film and the tracing paper. After that, hard and tissue landmarks will be traced onto the tracing paper manually using a HB pencil. A total of 11 anatomical landmarks will be plotted on each cephalograms which are the A point (subspinale, or A), B point (B), sella (S), nasion (N), orbitale (O), porion (Po), anterior nasal spine (ANS), posterior nasal spine (PNS), gonion (Go), menton (Me) and pogonion (Pog).

Measurements of the cephalometric parameters (8 angular and 8 linear) will be taken with the help of millimetre ruler and a protractor. All measurements will be performed twice by the same investigator with intervals of 4 weeks from the first measurements. Angular measurements ($^{\circ}$) include the SNA, SNB, ANB, FMPA, MMPA, UIA, LIA, IIA. While the linear measurements (mm) include the NA, NPog, ANS-Me, SN, LFH, UFH, MxPI, MnPI.

Table 1: Definition of the relevant cephalometric points

Cephalometric points	Definition
Point A (A)	The deepest point in the concavity of the anterior maxilla between the ANS and alveolar crest
Point B (B)	The deepest point in the concavity of the anterior mandible between the alveolar crest and Pog
Sella (S)	The midpoint of sella turcica
Nasion (N)	Junction of the frontal and nasal bones at the frontonasal suture
Orbitale (O)	The most inferior point on the infra- orbital margin
Porion (Po)	The most superior point of the external auditory meatus
Anterior Nasal Spine (ANS)	The anterior limit of the nasal floor
Posterior Nasal Spine (PNS)	The posterior limit of the nasal floor
Gonion (Go)	The most posterior and inferior point on the angle of the mandible
Menton (Me)	The most inferior point on the bony chin
Pogonion (Pog)	The most anterior point on the bony chin

For AI-based fully automated cephalometric analysis, we will be utilizing the WeDoCeph (Audax d.o.o., software version 3.2.2). WeDoCeph software is a fully automated cephalometric portal that works on the web and can be used anytime and from anywhere. WeDoCeph software complies with essential landmark tracing and measurement. To operate the analyses, firstly lateral or periapical radiographs of the patients will be uploaded into the WeDoCeph software. Then, patient profile will be created in the system and digital images of cephalograms with high quality resolution of 300DPI will be uploaded. After the x-ray was uploaded, key-in the analysis' parameters such as analysis type, patient's identifier, age and sex. Each of the cephalometric landmarks will automatically be traced by the AI digitization of

WeDoCeph. Finally, the cephalometric measurements value will be obtained for the different parameters and the tracing analysis were saved as JPEG files. Then, it will be downloaded in portable document format (pdf) and entered into the same Microsoft Office Excel spreadsheet used for manual tracing values. The same process will be applied for all 40 digital cephalograms. Then, all of the radiographs measurements will be performed once again by the same investigator with intervals of 4 weeks from the first measurements to test for the reliability.

[figure not shown]

Figure 1: Landmarks through AI-based fully automated tracing software.

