1.3 Research Hypothesis

1. The accuracy of AI-based cephalometric analysis is comparable to the conventional manual cephalometric tracing method.
2. The reliability of AI-based cephalometric analysis is better than the conventional manual cephalometric tracing method.

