2.2 Manual Tracing Vs Web-Based AI Program Cephalometric

Manual cephalometric analysis consumes valuable time due to the tedious procedures associated with it. The risks include misreading values and the measurements obtained may be susceptible to error (P Hlongwa, 2019). The reliability of the landmark identification is also questionable as it is hard to locate the tips of the caliper exactly on to the same point during every measurement to achieve consistency result (Umut Ozsoy et al,

2009). Based on the observer's experience, manual tracing can take 15-20 minutes to complete depending on the quality of the radiographs and the number of parameters assessed (Aravind K.S et al, 2022). In addition, manual tracing technique requires the printing of radiographic films and are more prone to poor quality printing and are susceptible to magnification errors (H. Alqahtani, 2020).

To overcome these problems, AI-based fully automated cephalometry was developed. Automated cephalometric analysis is one of the major applications of AI in the field of orthodontics. In recent years, various automated cephalometric software has been developed like CephX, WeDoCeph, CHEFBOT and WebCeph which utilizes artificial intelligence for automatic landmark identification instead of manual identification (Ravi K.M et al, 2022). This can significantly reduce the time and improve the efficiency of orthodontists in carrying out cephalometric analysis and diagnosis in routine clinical practice and research. Errors due to faulty identification of landmarks can result in inaccurate cephalometric interpretation which might lead to errors during orthodontic diagnosis and treatment planning.

The term AI is mostly associated with robotics which describes the development of software or machine by technology that can easily mimic human cognitive skills and perform specific activities (Sanjeev B.K, 2021). AI is now being used more frequently in orthodontics as it helps in data mining, automated diagnostics, and landmark detection of craniofacial morphometric studies. AI can identify landmarks as accurately as human examiners and it is a viable choice for a repeated recognition of numerous cephalometric landmarks. These AI-based fully automated cephalometry are gaining popularity among orthodontists because of their ability to obtain the information of patients quickly and has significantly influenced image analysis as it helps detect the anatomical landmark points consistently.

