3.5 Data Analysis

The mean, standard deviation, and standard error of the difference between the repeated measurements for each method and between the two methods will be calculated. The reliability of each method will be defined using the Pearson correlation coefficient (r^2). The level of statistical significance will be set at $P < 0.05$.

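### Hypothesis 2 claims better AI reliability, but the plan never compares the two reliabilities, and the two repeats capture different sources of variation

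*Combined protocol and SAP*

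**What the plan says.** Section 1.3 states the second hypothesis as a direction: "The reliability of AI-based cephalometric analysis is better than the conventional manual cephalometric tracing method".

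Section 3.4 describes a repeat for each method.

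- **Manual.** Landmarks are plotted by hand and read with ruler and protractor. "All measurements will be performed twice by the same investigator with intervals of 4 weeks from the first measurements". Whether the tracing is redone, or the first tracing is only remeasured, is not stated.
- **AI.** "Each of the cephalometric landmarks will automatically be traced by the AI digitization". The investigator's part is to upload the image, "key-in the analysis' parameters such as analysis type, patient's identifier, age and sex", and see that results are "entered into the same Microsoft Office Excel spreadsheet used for manual tracing values". For the repeat, "all of the radiographs measurements will be performed once again by the same investigator with intervals of 4 weeks from the first measurements". Whether the same file is uploaded again is not stated. Section 2.2 notes that the software has tools for moving landmarks; section 3.4 neither plans nor forbids their use.

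Section 3.5 defines reliability separately for each method by Pearson r². It adds that the mean, standard deviation and "standard error of the difference between the repeated measurements for each method and between the two methods will be calculated", with significance at P < 0.05. In section 4.0, Table 2 has an r² column for each method and one P-value per row, whose test is not named. Table 3 is a shell for an intraclass correlation with a 95% confidence interval and an F test against 0. It names no method, variable or model.

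**The concern.** A claim that one method is more reliable needs a comparison of the two reliabilities and a rule for reading it across the 16 parameters. The plan has neither. What it leaves is two r² columns side by side, which invites ranking by eye.

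The ranking is hard to interpret because the two repeats are exposed to different errors. The manual repeat carries the investigator's reading error, and tracing error too if the tracing is redone. The AI repeat carries whatever changes when an automated program is run again: the file, the software version, the keyed inputs, any landmark edit and the transfer to Excel. If none of these changes, a high AI r² shows only that the program gives the same answer twice. The report could then present the absence of operator variation as evidence of a better method. Section 2.2 credits AI because "it helps detect the anatomical landmark points consistently". That may be a real advantage, but identical output on an identical image says nothing about landmark quality or about performance on a new image of the same patient.

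**Working it through.** **The plan's own figure.** The only stated calculation is the minimum of 37 radiographs at significance level 0.05 and 95% power (section 3.1). It cannot be reproduced, because no effect size, SD, test or sidedness is given. Solving backwards, 37 fits a paired t test at a standardised difference of 0.609 (two-sided) or 0.551 (one-sided), or a test of a correlation against 0 at r = 0.55 or 0.51. None of these contrasts two reliabilities.

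**Inputs.** From the documents: n = 40 radiographs, two repeats, 16 parameters. Assumed: between-radiograph SD S = 3 to 5 units, manual within-radiograph SD s = 0.5 to 1.5 units, keying error e = 5 to 10 units.

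**1. AI output unchanged (assumption).** AI repeat SD = 0 and r² = 1. For manual, r = S²/(S² + s²), so:
- S = 3, s = 1.5: r = 9/11.25 = 0.800, r² = 0.640
- S = 4, s = 1: r = 16/17 = 0.941, r² = 0.886
- S = 5, s = 0.5: r = 25/25.25 = 0.990, r² = 0.980

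AI is higher over the whole range, as any value below 1 must be.

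**2. AI output unchanged, but one of 40 values mis-keyed.** r² = S²/(S² + e² × (1/40) × (39/40)), so:
- S = 5, e = 5: 25/25.609 = 0.976
- S = 4, e = 10: 16/18.4375 = 0.868
- S = 3, e = 10: 9/11.4375 = 0.787

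The AI within-radiograph SD becomes e/√40/√2 = 0.56 (e = 5) or 1.12 (e = 10), inside the range assumed for manual. The figure would then describe data entry.

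**3. Equal repeat error.** With S = 4 and the same within-radiograph SD for both methods (0.25 to 1.5), AI had the higher r² in 48% to 51% of 4,000 simulated data sets per setting. At one half per row, 16 × 0.5 = 8 rows would favour AI by chance.

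**4. What a test against 0 can show.** At n = 40 the two-sided 5% critical r is 0.312, so r² = 0.097 is enough. For the intraclass correlation (two-way model assumed), critical F(39,39) = 1.704, and (1.704 − 1)/(1.704 + 1) = 0.260 for single measures. Passing either threshold does not rank the methods.

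**5. What 40 radiographs can support.** The 95% interval for a within-radiograph SD (39 df) runs from 0.819 to 1.284 times the estimate. If all 40 outputs are identical, the exact 95% lower bound is 0.025^(1/40) = 91.2%. An approximate two-sided 5% F test on the ratio of repeat-difference SDs, treating the methods as independent, has power of about 28%, 71%, 93% and 99% for ratios of 1.25, 1.5, 1.75 and 2.0. This is for one parameter without multiplicity adjustment. A formal contrast is therefore feasible if the AI SD is above 0.

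**The case against.** The strongest reply is that the asymmetry is the research question. Section 1.1 names human fatigue and measurement error as the problem. A method that removes operator variation is more repeatable as used, and a test-retest of each workflow is legitimate. Unchanged output from a web portal after four weeks is also a result. All of this stands. It does not supply the missing comparison, and it limits what the result means: repeatability of each workflow on the same image.

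A reader might infer that AI r² is bound to be 1 and the outcome fixed in advance. The documents do not support that. They do not say that the software returns identical output or that the same file is reused, and landmark editing is left open. Step 2 shows that AI r² can fall well below 1.

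A reader might also take the F test in Table 3 as the plan's test of Hypothesis 2. The plan does not say so. The table also carries a confidence interval, and it could refer to agreement between methods or to the examiner calibration in section 3.4. Similarly, the between-method differences in section 3.5 are differences in measured values, which bear on the accuracy objective. They are not a contrast of repeat errors.

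**Conclusion.** The concern holds in a limited form and should be fixed. It is certain from the text that Hypothesis 2 is directional and that sections 3.5 and 4.0 contain no contrast, interval or rule comparing the two reliabilities. It is also clear that the repeats are exposed to different sources of variation.

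The size is conditional. With an unchanged file, no edits and unchanged output, AI r² is 1 against 0.64 to 0.98 for manual. With one keying error it is 0.98 to 0.79. With equal repeat error the ranking is a coin toss. The SDs and the keying error are assumed, not taken from the documents.

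Two further inferences go too far: that the comparison of workflows is invalid, and that a descriptive Hypothesis 2 is the only remedy. Each repeat estimates something useful, the manual error above all, and a prespecified contrast is a workable alternative. Accuracy is a separate objective and is not affected by this point.

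**What to change.** 1. **Section 3.4.** State whether the AI repeat uploads the same file, whether landmark edits are allowed, and whether the manual tracing is redone or only remeasured. At each AI run, log the file, software version, keyed inputs and any edit. Check the Excel entries against the downloaded PDFs, so that keying errors are separated from software variation.
2. **Section 3.5.** For each parameter, report each method's within-radiograph SD (repeat-difference SD divided by √2) with a 95% confidence interval, the share of identical AI outputs with an exact interval, and the largest difference. If the AI SD is 0, the share of identical outputs takes the place of its interval. Do not rank the methods on r² or on a test against 0. Define the Table 2 P-value, and name the method, variable and model for Table 3.
3. **Section 1.3.** Either restate Hypothesis 2 as descriptive, or prespecify one paired between-method contrast and a rule across the 16 parameters. The ratio or difference of within-radiograph SDs with a paired bootstrap interval would serve; the difference stays usable if the AI SD is 0.
4. **Interpretation, in either case.** Describe the result as repeatability of each workflow on the same image, not as evidence of AI landmark quality or of robustness to new images.

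The cost is text changes, a short log and a check of 40 × 16 × 2 = 1,280 AI values. No new radiograph, reader or exposure is needed. The downside is a weaker claim about AI reliability.

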3.5 Data Analysis

The mean, standard deviation, and standard error of the difference between the repeated measurements for each method and between the two methods will be calculated. The reliability of each method will be defined using the Pearson correlation coefficient (r^2). The level of statistical significance will be set at $P < 0.05$.

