Cephalometric analysis aids in evaluating dentofacial proportions, identifying the anatomic basis of malocclusion and analysing growth and treatment-related changes. During orthodontic treatment planning, cephalometric analysis is considered an essential diagnostic method, particularly when a skeletal discrepancy exists. The introduction of Artificial Intelligence (AI) in orthodontics solved a variety of issues as it has been evidenced to be a time-saving and reliable tool to assist in developing correct diagnosis and successful treatment plans. Computerized software can automatically identify the landmarks and complete the measurements once the digital radiograph is imported using AI technology. In addition, superimposition of serial radiographs can be performed faster, and it also allows the user to obtain several analyses at a time, identify and analyse cephalometric landmarks, face analysis, tooth and mandible segmentation, bone age determination, prediction of orthognathic surgery, and temporomandibular bone segmentation. As a result, AI is increasingly being used in orthodontic treatment to improve speed, consistency, and accuracy because it is a promising tool for facilitating cephalometric tracing in routine clinical practice and analysing large databases for research purposes. Hence, it is imperative to investigate the reliability and usability of AI in cephalometric to ensure its accuracy before relying on the software for analysis.

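### Section 3.5 plans no check of whether the AI–manual difference depends on the size of the measurement

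*Combined protocol and SAP*

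**What the plan says.** Section 3.5 is the whole analysis plan. Its first sentence lists the mean and the SD, and continues: "standard error of the difference between the repeated measurements for each method and between the two methods will be calculated". All three statistics thus apply both to the repeats within a method and to the AI–manual comparison. The Pearson coefficient is assigned to the reliability of each method, so it does not measure agreement between AI and manual values.

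Table 2 in section 4.0 has columns for the mean, SD and r² of each method and one P-value per parameter, from a test that is not named. Table 3 is an empty intraclass correlation table; its form and the pair of measurements it compares are not stated.

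The documents plan no plot of difference against level, no slope, no comparison of the two methods' SDs and no breakdown by skeletal pattern. Hypothesis 1 in section 1.3 is that AI accuracy is comparable to manual tracing, with no margin. The opening summary says that "cephalometric analysis is considered an essential diagnostic method, particularly when a skeletal discrepancy exists". Section 3.3 excludes syndromes and craniofacial deformities, but not ordinary skeletal discrepancy.

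**The concern.** A mean difference describes the bias well only if the bias is much the same at every value of the parameter. One plausible failure of automated tracing is that it pulls unusual faces toward a typical one. High values then read too low and low values too high, and the two errors offset each other in the mean.

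The study could then report no difference between methods, and count this toward Hypothesis 1, while the AI was systematically wrong on the films for which the summary says the analysis matters most. Nothing planned would separate that case from true agreement with random error.

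**Working it through.** **Inputs from the documents.** Forty films, each measured by both methods; manual readings made twice by the same investigator, 4 weeks apart; 16 parameters; significance level 0.05. The stated minimum ("A sample of a minimum of 37 radiographs was needed") cannot be reproduced, because no effect size, SD, test or sidedness is given. Working backwards at 95% power, a two-sided paired t-test needs 37 films for a standardised difference of 0.61 (39 for 0.60, 54 for 0.50). That concerns a mean difference and says nothing about a slope.

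**Assumed inputs, none from the documents.** For ANB: between-film SD 3 degrees; manual error SD 0.7 per reading; AI slope b = 0.8 on the true value; AI error SD 0.8 or 1.5 degrees. The manual value is taken as the mean of the two readings, with error variance 0.7²/2 = 0.245, and the between-method test as a paired t-test.

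**Step 1, error on one film.** A film at distance d from the value c to which the AI shrinks is wrong by (1 − b) × d in size. At d = 6 this is 0.2 × 6 = 1.2 degrees.

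**Step 2, what the planned mean and SD show.** If the sample mean lies k degrees from c, the expected mean difference is 0.2 × k in size. The SD of the difference is √[(1 − b)² × 9 + 0.245 + AI error variance].

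| AI error SD | SD of difference, b = 1 | SD of difference, b = 0.8 | t-test rejects, k = 0 | k = 1 | k = 2 |
|---|---|---|---|---|---|
| 0.8 | √0.885 = 0.94 | √1.245 = 1.12 | 5% | 20% | 60% |
| 1.5 | √2.495 = 1.58 | √2.855 = 1.69 | 5% | 11% | 31% |

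Sample SDs from 40 films average slightly lower: 0.93 to 1.11, and 1.57 to 1.68. A rise of this size looks the same as a little more random error.

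**Step 3, what the SDs in Table 2 show.** The AI/manual SD ratio is √[(b² × 9 + AI error variance)/9.245].
- b = 0.8, AI error SD 0.8: √(6.40/9.245) = 0.83
- b = 0.8, AI error SD 1.5: √(8.01/9.245) = 0.93
- b = 0.9, AI error SD 1.5: √(9.54/9.245) = 1.02

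AI noise can cancel the trace completely.

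**Step 4, a slope analysis.** Regress the AI value on the manual mean, then divide the slope by the reliability of the manual mean, estimated from the repeats (here 9/9.245 = 0.973). Simulated studies of 40 films, 8,000 runs:

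| True slope | Rejects slope = 1, AI error SD 0.8 | AI error SD 1.5 |
|---|---|---|
| 1.0 | about 5% | about 5% |
| 0.9 | about 50% | 21% |
| 0.8 | 96% | 63% |

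Regressing the difference on the AI–manual average instead gives about 24% false rejections at true slope 1 and AI error SD 1.5, because the two methods then have unequal error.

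**Step 5, other inputs.** With true SD 2.5 or 4.0, equal error SD of 0.75 or 1.5 for each method, and a sample centred on c, the mean-difference test rejects in about 5% of studies for every b from 0.9 to 0.5. A test of difference against average, which is fair when the errors are equal, has power 0.25 to 0.99 at b = 0.8 and 0.10 to 0.62 at b = 0.9.

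**The case against.** A reader might infer that accuracy rests on one average per parameter and that the plan is blind to shrinkage. The documents do not support that. The same sentence of section 3.5 plans the SD of the difference, from which limits of agreement follow (though the plan does not say they will be reported), and Table 2 sets the two methods' SDs side by side. Step 3 shows that this leaves a visible trace in some cases. What stands against the objection is that the trace is undependable and no comparison is planned.

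The 5% rejection rate is also a worst case. It needs a sample centred where the AI shrinks to, and patients of a specialist clinic need not be. Off centre, the test gains power, but a significant mean would still be read as a constant bias.

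A reader might also infer that this software does shrink values. No passage says so; the slope and all the SDs are assumed.

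The remedy has limits too. The same investigator makes both manual readings, so a landmark misplaced the same way twice is absent from the repeat variance. With persistent error SD 0.7 or 1.0, a true slope of 1 is pulled to 9/9.49 = 0.95 or 9/10 = 0.90, and a test of slope = 1 rejects falsely in about 14% or 29% (AI error SD 0.8). Over 16 parameters, a rule based on the CI excluding 1 would raise at least one false flag with probability 1 − 0.95¹⁶ = 56% if the parameters were independent; they are correlated, so the true figure differs. These points rule out an accept/reject rule, but not the estimate.

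**Conclusion.** The gap is real and moderate, and worth closing. Section 3.5 has no check of whether the AI–manual difference depends on the level of the measurement, and neither the planned SD of the difference nor the SDs in Table 2 can stand in for one. Under the assumed ANB inputs, a 1.2-degree error on a film 6 degrees from the centre goes with a mean-difference test that rejects in anything from 5% to 60% of studies, depending on how the sample is centred and on AI error. The corrected slope finds the same shrinkage in 96% or 63%. Milder shrinkage is often missed with 40 films, so the CI matters more than the P-value. The absence of a check is read directly from the documents; the size of the consequence rests on assumed inputs.

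**What to change.** Add to section 3.5:

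> For each parameter the AI–manual difference is plotted against the level of the measurement with 95% limits of agreement. The slope of the AI value on the mean of the two manual readings, corrected for manual error using the repeat variance, is reported with its 95% CI, together with the predicted AI–manual difference at the 10th and 90th percentiles of the films. The conclusion on Hypothesis 1 takes these predicted differences into account and does not rest on the mean difference alone.

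State as well that the slopes are descriptive estimates across 16 parameters, with no decision rule based on the CI excluding 1, and that the correction does not remove errors the same investigator repeats on both readings, which can pull the slope below 1.

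The cost is a small amount of extra analysis and some extra table columns. The paired films and repeat readings are already planned.

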4.0 Expected Outcome

Table 2: Angular and Linear Measurement of Cephalometric Values

Measurements	AI-based (WeDoCeph)			Manual			P-value
	Mean	S.D	r²	Mean	S.D	r²	
SNA (°)	n	n	n	n	n	n	n
SNB (°)	n	n	n	n	n	n	n
ANB (°)	n	n	n	n	n	n	n
FMPA (°)	n	n	n	n	n	n	n
MMPA (°)	n	n	n	n	n	n	n
UIA (°)	n	n	n	n	n	n	n
LIA (°)	n	n	n	n	n	n	n
IIA (°)	n	n	n	n	n	n	n
A-N perpendicular (mm)	n	n	n	n	n	n	n
POG-N perpendicular (mm)	n	n	n	n	n	n	n
ANS-Me perpendicular (mm)	n	n	n	n	n	n	n
SN (mm)	n	n	n	n	n	n	n
LFH (mm)	n	n	n	n	n	n	n
UFH (mm)	n	n	n	n	n	n	n
MxPI (mm)	n	n	n	n	n	n	n
MnPI (mm)	n	n	n	n	n	n	n

Table 3: Intraclass Correlation Coefficient

Intraclass Correlation	95% Confidence Interval			F Test with True Value 0			
	Lower Bound	Upper Bound	Value	df1	df2	sig	
Single Measures							
Average Measures							

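### Section 3.5 defines reliability by a Pearson coefficient, mislabelled r², that cannot register a systematic shift between the two readings, and it never mentions the ICC in Table 3

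*Combined protocol and SAP*

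**What the plan says.** Hypothesis 2 (section 1.3) is comparative: "The reliability of AI-based cephalometric analysis is better than the conventional manual cephalometric tracing method". Section 3.4 supplies data for it. For manual tracing, "All measurements will be performed twice by the same investigator with intervals of 4 weeks from the first measurements"; the AI runs are also repeated, "with intervals of 4 weeks from the first measurements to test for the reliability".

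Section 3.5 then gives the definition: "The reliability of each method will be defined using the Pearson correlation coefficient (r^2". The sentence before it commits to the mean, SD and "standard error of the difference between the repeated measurements for each method", and to the same summaries between methods, but does not call these reliability and sets no limit for them.

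Section 4.0 has two relevant table shells. "Table 2: Angular and Linear Measurement of Cephalometric Values" gives each method a mean, an SD and an r². The r² is the only reliability column, and no column is labelled for repeat differences. Table 3 is an ICC shell with rows for single and average measures. It names no method, parameter or model, and does not say whether the ICC is for agreement or consistency. Section 3.5 does not mention an ICC.

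**The concern.** Three things are wrong as written.

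- **The statistic.** Two sets of readings can correlate almost perfectly and still differ by a constant. A change in tracing habit over the 4 weeks would be such a difference, and r would not show it.
- **The label.** Pearson's coefficient is r. The symbol r² is its square, so a reader cannot tell which will be reported.
- **The tables.** The plan carries two reliability statistics, r² in Table 2 and an ICC in Table 3, without saying how they relate. Pointing to Table 3 would not be enough, because a consistency ICC ignores a constant shift just as r does.

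At stake is the AI-manual comparison in Hypothesis 2. The coefficient can overstate the reliability of a method that drifts, and so misstate the gap between the methods.

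**Working it through.** **Inputs.** From the documents: 40 radiographs (sections 3.1 and 3.4) and two readings per method, 4 weeks apart (section 3.4). The plan gives no reliability figure to reproduce. Assumed, because the documents give no values: between-patient SD b = 3, 4 or 6°; random error SD per reading e = 0.5, 0.7 or 1.0°; constant shift s = 0 to 3°. Degrees are for illustration; the same formulas apply in mm to the eight linear parameters.

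**Step 1, invariance.** r = cov(X1, X2) / [SD(X1) × SD(X2)]. Replacing X2 by X2 + s changes neither the covariance nor the SDs, so r and r² are unchanged. This needs no assumption.

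**Step 2, what an ICC does.** The absolute-agreement, single-measure ICC is approximately b² / (b² + e² + s²/2). With b = 4 and e = 0.5:

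- s = 0: 16 / (16 + 0.25) = 0.985
- s = 1: 16 / (16 + 0.25 + 0.5) = 0.955
- s = 2: 16 / (16 + 0.25 + 2) = 0.877

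The consistency ICC has no s term and stays at 0.985. Medians over 20,000 simulated sets of 40 pairs:

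| b, e | r, any shift | ICC at 0° | 0.5° | 1° | 2° | 3° |
|---|---|---|---|---|---|---|
| 3, 0.5 | 0.974 | 0.973 | 0.960 | 0.922 | 0.797 | 0.65 |
| 4, 0.5 | 0.985 | 0.985 | 0.977 | 0.955 | 0.875 | 0.77 |
| 6, 0.5 | 0.993 | 0.993 | 0.990 | 0.979 | 0.941 | 0.88 |
| 4, 1.0 | 0.942 | 0.941 | 0.934 | 0.914 | 0.841 | 0.74 |

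A 0.5° shift costs at most 0.973 − 0.960 = 0.013. A 1° shift costs from 0.993 − 0.979 = 0.014 to 0.973 − 0.922 = 0.051.

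**Step 3, the label.** 0.985² = 0.970 and 0.902² = 0.814. Over that range, reporting r or r² alone moves the value by 0.015 to 0.09.

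**Step 4, the comparison of methods.** Section 2.2 says of manual work that "it is hard to locate the tips of the caliper exactly on to the same point during every measurement" and of AI that "it helps detect the anatomical landmark points consistently". If that holds, r orders the methods correctly.

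- *AI repeats identical, manual drifts* (b = 4, manual e = 0.5). The AI value is 1 on either statistic. The gap on r is 1 − 0.985 = 0.015 at every shift. On the ICC it is 0.015, 0.023, 0.045, 0.125 and 0.23 at 0, 0.5, 1, 2 and 3°. So r understates the gap but does not reverse it.
- *The drifting method has the smaller random error* (b = 4, errors 0.5 against 0.7). Here r prefers the drifting method in 98% of runs at every shift. The ICC does so in 98, 80, 48, 7 and 0% at 0, 0.5, 0.7, 1 and 2°. The break-even shift is √[2 × (0.7² − 0.5²)] = √0.48 = 0.69°.
- *Equal errors of 0.5*. r prefers the drifting method in 50% of runs; the ICC does so in 10% at 0.5° and 0% at 1°.
- *The drifting method has the larger error* (0.7 against 0.5). r prefers it in 2% of runs, and the ICC in 0% at 1 to 2°. The two statistics agree.

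**Step 5, the planned repeat difference.** Its 95% CI half-width is 2.02 × √2 × e / √40, which is 0.23, 0.32 and 0.45° for e = 0.5, 0.7 and 1.0. It shows a shift directly and precisely, but section 3.5 does not make it part of reliability.

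**The case against.** The strongest reply is that the plan would see a shift anyway. The mean repeat difference is already to be computed for each method. A two-sided 5% paired t-test on it, with 40 pairs, has power above 99.9% for the 0.69° break-even shift when the error is 0.5°, 99% when it is 0.7° and 85% when it is 1.0°. The weak spot, a 0.5° shift with 1.0° error (power 59%), costs the ICC only 0.941 − 0.934 = 0.007. An ICC table is also foreseen. No drift is documented, and section 3.4 has one named software version tracing automatically, so near-identical AI repeats are plausible; reversal would then be impossible. If manual tracing is what drifts, r is conservative for Hypothesis 2. Finally, r and r² rank the methods alike when r is positive.

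Most of this stands, and it limits the weight of the point. A large shift would probably be visible somewhere in the output, and the reversal is a narrow case that should not carry the argument. It does not rescue the definition: the statistic named for Hypothesis 2 would still ignore the shift that another planned summary showed, and nothing says which would govern the conclusion. The labelling error and the unlinked Table 3 need no drift at all.

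**Conclusion.** The concern holds and should be fixed. The statistic that defines reliability is wrongly chosen and mislabelled, and the ICC shell is not linked to it. The invariance of r and the difference between r and r² are algebraic; all the sizes rest on assumed SDs and shifts. On those assumptions the overstatement is negligible at 0.5°, about 0.01 to 0.05 at 1°, and about 0.05 (0.993 − 0.941) to 0.18 (0.973 − 0.797) at 2°. A wrong ranking of the methods requires that the drifting method have equal or smaller random error and that the shift be large enough. It cannot happen if the AI repeats are identical.

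**What to change.** - In section 3.5, replace the Pearson definition with a two-way, absolute-agreement, single-measure ICC and its 95% CI, for each parameter and each method. State whether sessions are treated as random or fixed (the point estimate is the same) and name the CI method.
- Beside it, report the already planned mean repeat difference with its 95% CI and SD, in degrees or mm.
- Replace the r² columns of Table 2 with these quantities. Give Table 3 the same ICC type and one line per parameter and method.
- If the AI repeats are identical, say so and report the manual error with its CI.
- Optionally, add the Dahlberg error and a bootstrap comparison of the two methods, which would address Hypothesis 2 directly.

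**Cost.** Wording and table shells only; no new readings. Reported reliability may be lower than r. The ICC depends on between-patient spread: at a 2° shift it is 0.80, 0.875 and 0.94 for SDs of 3, 4 and 6°. The CI method matters because there are only two sessions. At SD 4° and error 0.5°, the standard F-based interval is 0.97 to 0.99 with no shift but 0.36 to 0.99 at 1°. A percentile bootstrap over radiographs, which treats the two sessions as fixed, gives 0.92 to 0.97 at 1°. This is a further reason to keep the mean repeat difference beside the ICC.
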